4.3 Study Variables

4.3.1 Exposure

The exposure group will include children whose mother were prescribed an only monotherapy of macrolide antibiotics from 5 GW to delivery (hereafter, “during pregnancy”). A monotherapy is defined as one or more consecutive prescriptions for a single antibiotic (i.e. same drug substance) separated by no more than 30 days and uninterrupted by prescriptions for other antibiotic drug substances. The macrolides prescription is identified using a drug code list based on chapter 5.1.5 of the British National Formulary. The date of first prescription is used as the index date. The reference group includes children whose mothers were exposed to an only monotherapy of penicillins during pregnancy. Preliminary analysis shows that 81% of all antibiotic prescriptions were monotherapies. We further divide the time window into 1) 5GW to 13GW (29 Gestational Day [GD] to 91GD, hereafter, “1st trimester”), the critical period for most major malformation, and 2) 14GW to delivery (hereafter, “2nd–3rd trimester”).(21) The negative control cohort (see “4.4.2 Sensitivity analyses [1]”) includes children of mothers prescribed an only monotherapy of macrolides or penicillins during 10-50 weeks prior to conception and are not included in the study cohort.

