4.2 Study Population

The Mother-baby link includes 1,071,379 children born from Jan 1st 1990 to June 30th 2016.

Inclusion Criteria:

- Children whose mother was prescribed an only monotherapy of macrolide or penicillin during pregnancy (between 5 Gestational Week [GW] and delivery)
- Children who registered with the general practice (GP) within 6 months of birth
- Children whose mother was aged 14 to 50 years at delivery and had been registered with GP from at least 50 weeks before estimated conception date to delivery

Exclusion Criteria:

Children with known chromosomal abnormalities or with fetal exposure to known teratogenic medications (warfarin, angiotensin-converting enzyme (ACE) inhibitors, antineoplastic agents, isotretinoin, misoprostol, and thalidomide).

Children will be followed from birth to death, end of follow-up (June 30th, 2016), or age 14, whichever came first.

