- a Read codes for hypertension and associated diagnoses (including pre-eclampsia, eclampsia and HELLP syndrome), or
- a prescription for hypertension drugs from sections 2.2 and 2.5 of the BNF. This variable identified mothers with both treated and untreated hypertension in pregnancy.

7) **Diabetes**

Measurement from 50 weeks prior to delivery:

- a Read code for type I, type II, or gestational diabetes;
- two or more prescriptions for anti-diabetic medication; or
- laboratory tests indicative of diabetes (defined as ≥ 2 abnormal glucose tests, fasting glucose >7.0 millimoles per litre [mmol/L] or >126 milligrams per decilitre

[mg/dL], plasma glucose after glucose tolerance test >11.1 mmol/L or 200mg/dL, glycated haemoglobin \geq 6.5%, or with diabetes annual review).

8) Epilepsy

Measurement from 50 weeks prior to delivery: 2 prescriptions of antiepileptic drugs (AEDs) within 4 months or \geq 1 diagnosis

9) Depression

Measurement from 50 weeks prior to delivery: \geq 2 occurrences of diagnostic code, treatment code or symptom

10) Anxiety

Measurement from 50 weeks prior to delivery: \geq 2 occurrences of diagnostic code, treatment code or symptom

11) Treatment of chronic medical conditions during pregnancy

Measurement during pregnancy: two or more prescriptions (on separate days during pregnancy and not more than four months apart) for drugs from the same BNF section or paragraph. Drugs used to treat common conditions in pregnancy such as reflux (BNF section 1.2), nausea and vomiting (BNF section 4.6), and constipation (BNF section 1.3) were not included.

12) Potentially fetal-damaging infections during pregnancy.

Mothers are classified as having a potentially fetal-damaging infection in pregnancy if they had recorded at any time during their pregnancy, a Read code for a diagnosis or a laboratory test confirming any of the following infection: genitourinary infection, "TORCH" (Toxoplasmosis, Other agents such as HIV, Rubella, Cytomegalovirus and Herpes simplex) and sexually transmitted infections (STIs). "TORCH" and STIs have long been known as important risk factors to adverse pregnancy outcomes and teratogenic pathogens. (22, 23) Intrauterine infection has been recognised as an important mechanism of disease in preterm labor. (24) Hyelonephritis and bacteriuria have also been linked with preterm labor and low birthweight. (25)

3. Neonatal variables

13) Baby gender

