4.4 Analyses

4.4.1 Statistical methods

Standardized differences will be used to assess covariate balance between the macrolides group and the penicillins group; meaningful imbalances are defined by an absolute standardized difference of more than 0.1.(30) For neurodevelopmental disorders, absolute rates of outcomes and unadjusted hazard ratios with 95% confidence intervals will be calculated. For malformations, absolute risks of outcomes and unadjusted risk ratios with 95% confidence intervals, will be calculated. Exposure propensity scores will be estimated as the predicted probability of receiving the macrolides prescription (vs. penicillins), conditional on the covariates described above, with the use of logistic-regression models. For each estimated propensity score, the population in the nonoverlapping areas of the propensity-score distributions will be trimmed, and 50 strata will be created on the basis of the distribution of the treated women.(31) Weights for the reference group will be calculated according to the distribution of the treated women among propensity-score strata. We then use the weight to estimate adjusted baseline characteristics, and adjusted hazard ratios (in Cox proportional hazard models with weight statement for neurodevelopmental disorders) or risk ratios (in log-binomial model with weight statement for malformations) as well as their 95% confidence intervals. To account for the clustering of siblings and multiple births within mother, robust standard errors will be estimated. The analyses will be conducted using RStudio version 3.5.1.. No adjustment will be made for multiple comparisons, and results for comparisons of exposure timing and subgroup analysis should be interpreted as exploratory.

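### As written, the negative-control cohort can keep mothers with repeated or mixed macrolide courses in pregnancy; report exposure by arm and show sensitivity analysis 1 with and without them

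*Combined protocol and SAP*

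**What the plan says.** Section 4.3.1 (Exposure) defines the negative control as children of mothers "prescribed an only monotherapy of macrolides or penicillins during 10-50 weeks prior to conception and are not included in the study cohort". Those are its only two conditions.

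The study cohort, from which the control is kept apart, has the entry criterion "Children whose mother was prescribed an only monotherapy of macrolide or penicillin during pregnancy" (section 4.2), with pregnancy counted from 5 gestational weeks (GW) to delivery. Section 4.3.1 defines a monotherapy as "one or more consecutive prescriptions for a single antibiotic (i.e. same drug substance) separated by no more than 30 days", and requires that it be "uninterrupted by prescriptions for other antibiotic drug substances".

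Section 4.4.2, sensitivity analysis 1, compares macrolides with penicillins in the preconception window in order to gauge confounding by maternal baseline characteristics. It sets no condition on antibiotics taken in pregnancy and promises no report of them.

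Three other statements bear on the point:
- Section 4.3.3, item 11, flags "two or more prescriptions (on separate days during pregnancy and not more than four months apart) for drugs from the same BNF section" or paragraph.
- Section 4.4.1 estimates the propensity score "conditional on the covariates described above".
- Section 4.3.1 adds: "Preliminary analysis shows that 81% of all antibiotic prescriptions were monotherapies".

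**The concern.** A negative control of this kind is read as follows: the fetus was not exposed to the drug, so any ratio away from 1 points to differences between the mothers. That reading needs macrolide exposure in pregnancy to be absent from both arms or balanced between them.

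Being outside the study cohort is not the same as being unexposed. A mother can fail the single-monotherapy rule because she had more macrolide treatment than it allows. The rule then takes out pregnancies with one macrolide course and can leave in those with several. If women given a macrolide before conception are more (or less) likely than women given a penicillin to receive such courses in pregnancy, a true drug effect would appear in the control ratio and could be taken for confounding, or could mask it. A reader who is not shown exposure by arm cannot tell.

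**Working it through.** **Step 1. Who is eligible.** Take a mother with a qualifying preconception monotherapy who meets the other entry criteria, and apply the definitions in sections 4.2 and 4.3.1 to her antibiotics from 5 GW to delivery.

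| Antibiotics in pregnancy | In study cohort | Eligible for control |
|---|---|---|
| None | No | Yes |
| One macrolide course (repeats up to 30 days apart count as one) | Yes | No |
| Two courses of one macrolide, more than 30 days apart | No | Yes |
| Two different macrolide substances | No | Yes |
| A macrolide and another antibiotic | No | Yes |

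The last three rows are the gap.

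**Step 2. Effect on the control ratio.** The documents give neither the size of the control nor in-pregnancy exposure within it, so there is no stated figure to reproduce and all shares below are assumptions. Let a and b be the shares with macrolide exposure in pregnancy in the preconception macrolide and penicillin arms, and R the true risk ratio. With no confounding and no adjustment,

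control ratio = (1 + a(R − 1)) / (1 + b(R − 1)).

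| a vs b | R = 2 | R = 1.5 |
|---|---|---|
| 3% vs 1% | 1.03/1.01 = 1.020 | 1.015/1.005 = 1.010 |
| equal shares | 1.000 | 1.000 |
| 1% vs 3% | 1.01/1.03 = 0.981 | 1.005/1.015 = 0.990 |
| 20% vs 5% (extreme) | 1.20/1.05 = 1.143 | 1.10/1.025 = 1.073 |

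**Step 3. Malformations.** Section 4.3.1 calls 5-13 GW "the critical period for most major malformation". That window is gestational days 29-91, or 63 days. With delivery at day 280 (assumed), pregnancy from 5 GW covers 252 days. If courses fall evenly over those days, the chance f that at least one falls in the window is:
- one macrolide course: 63/252 = 0.25
- two independent courses: 1 − 0.75² = 0.44
- two courses more than 30 days apart: of 24,531 possible day pairs, 12,561 miss the window, so 1 − 12,561/24,531 = 0.488

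Replacing a and b by fa and fb, with R = 2 and 3% vs 1%:
- f = 0.25: 1.0075/1.0025 = 1.005
- f = 0.488: 1.01464/1.00488 = 1.010

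The extreme 20% vs 5% gives 1.04 to 1.07.

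**Step 4. Sampling error.** Assume the control has the study's approximate arm sizes from section 4.5 (10,000 and 100,000) and the baseline risks p in Table 2. The 95% confidence factor around a ratio of 1 is

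exp(1.96 × √[(1 − p)/(10,000p) + (1 − p)/(100,000p)]).

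- Any major malformation, p = 0.02: exp(1.96 × 0.0734) = 1.15
- Cerebral palsy, p = 0.002: exp(1.96 × 0.2343) = 1.58 (treated here as a risk ratio; the plan uses hazard ratios)

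A shift to 1.020 is 0.0196 on the log scale. That is 14% of the half-width for any malformation (0.0196/0.1439) and 4% for cerebral palsy (0.0196/0.4592).

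**The case against.** The case for leaving the plan alone has four parts.

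**Adjustment already exists.** Section 4.4.1 is the general methods section. Section 4.4.2 restates no method for any analysis, the primary one included. A reader might infer that sensitivity analysis 1 is unadjusted because it does not mention the propensity score, but the documents do not support that. Item 11 would therefore enter the score and flag two macrolide prescriptions within four months, so the unadjusted ratios above overstate what would remain. This stands, but only in part. Item 11 pools macrolides with every other repeatedly prescribed drug. It misses prescriptions more than four months apart, and it misses a single macrolide prescription paired with a single antibiotic from a different section or paragraph.

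**The larger scenario has no anchor.** About 10,000 macrolide pregnancies among 1,071,379 linked children is 0.9%. That counts single-course mothers over a denominator not restricted to eligible children, and earlier macrolide users may be treated more often, so it bounds nothing. Still, 20% vs 5% is far above the only signal available. It is kept here as an extreme illustration and carries no weight in the conclusion.

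**The effect is small.** This also stands: 1.02 would not be visible against the sampling error, and even 1.14 lies inside the factor of 1.15 for any malformation.

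**A restricted analysis has its own bias.** Excluding mothers by treatment in pregnancy can select on infection. Suppose 30% of each arm were treated for infection in pregnancy, at a risk ratio of 1.2 (both assumed). Removing 3% and 1% leaves treated shares of 0.27/0.97 = 0.278 and 0.29/0.99 = 0.293, and a true null moves to (1 + 0.2 × 0.278)/(1 + 0.2 × 0.293) = 0.997. This is a reason to show both versions. It is not a reason to withhold the exposure table, because the reassurance about size rests on assumed shares until that table exists.

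**Conclusion.** The point holds as a minor one. Followed exactly, the cohort rule can admit mothers with multiple or mixed macrolide courses in pregnancy to an analysis whose interpretation needs such exposure to be absent or balanced. Under assumed shares of 3% vs 1%, a true ratio of 2, no confounding and no adjustment, the control ratio would be about 1.02, or 1.005 to 1.010 for malformations if only 5-13 GW matters. Equal shares give 1.00, and reversed shares give 0.98. No primary estimate changes.

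Three stronger readings are tempting and not supported:
- **That the negative control is invalid or biased away from the null.** The documents show that such mothers can be included. They do not show that they will be, how many there are, or which arm has more. The authors may have meant to exclude all antibiotic use in pregnancy, though the text does not say so.
- **That 19% of mothers are affected, as the complement of the 81%.** That figure counts prescriptions, is not split by arm or drug, and counts each of two courses more than 30 days apart as a monotherapy. It shows that other prescribing patterns occur, and neither estimates nor bounds the share.
- **That a distortion of about 14% is to be expected.** That comes only from the unanchored 20% vs 5% case.

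**What to change.** 1. Report antibiotic exposure from 5 GW to delivery (macrolide, penicillin, other; number of courses) by arm of the negative-control cohort.
2. Present sensitivity analysis 1 twice: as planned, and excluding mothers with any macrolide prescription from 5 GW to delivery. The restricted version should accompany the planned one and not replace it, because of the possible selection on treated infection.

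The cost is one descriptive table and one repeat analysis, using windows and drug codes that section 4.3.1 already defines. Precision falls slightly. With 9,700 and 99,000 left of 10,000 and 100,000 (3% vs 1% removed), the standard error of the log ratio at p = 0.02 goes from √(0.98/200 + 0.98/2,000) = 0.0734 to √(0.98/194 + 0.98/1,980) = 0.0745, about 1.4% larger.

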4.3.2 Outcome

Based on previous evidence from experimental and epidemiological studies, we hypothesized that short-term fetal hypoxia induced by fetal arrhythmia could possibly be the underlying mechanism of observed adverse effects of macrolides.(22) We therefore include outcomes which could potentially result from short-term fetal hypoxia, i.e. neurodevelopmental disorders (CP, epilepsy, attention-deficit/hyperactivity disorder (ADHD) and autism spectrum disorder (ASD)) and major congenital malformation (malformation overall and system-specific malformations).

Neurodevelopmental disorders (CP, epilepsy, ADHD and ASD) are defined as the time to the first Read code or prescription indicating the outcomes by 14 years old. We have identified CP cases from informative prescription or Read codes using the Random Forest approach and were validated by a paediatric-neurologist blinded to the prenatal antibiotics exposure.(23) Other neurodevelopmental disorders (epilepsy, ADHD and ASD) will be identified with previously validated criteria using diagnostic codes and/or prescriptions (table 1). (24-26)

Major malformations will be identified from the European Surveillance of Congenital Anomalies (EUROCAT).(27) We will exclude musculoskeletal malformations (e.g. Club foot, knock-knee and hip dislocation) because they are not reliably recorded in GP records.(28) We also exclude children with known chromosomal abnormalities and children whose mother were exposed to known teratogenic medications (warfarin, angiotensin converting enzyme (ACE) inhibitors, antineoplastic agents, isotretinoin, misoprostol, and thalidomide). Any of the remaining 11 system-specific malformations are defined as major malformation overall, identified from child GP records up to 3 years old using Read codes which are mapped to the tenth edition of the International Classification of Diseases (ICD–10) code lists in EUROCAT (Table 1).(27) Five system-specific malformations (nervous, cardiovascular, digestive, genital tract, and urinary tract) were included which met the power criterion using the EUROCAT prevalence table.(29) (see “4.5 Power analysis”)

Table 1. Outcome identification.

Outcome	Case identification criteria
Cerebral palsy	Method based on predictor selection and prediction (23)
Epilepsy	2 prescriptions of antiepileptic drug (AED, identified based on British National Formula Chapter 4.8) within 4 months or ≥ 1 diagnosis
Attention deficit hyperactivity disorder (ADHD)	≥ 2 occurrence of prescriptions for ADHD (identified based on British National Formula Chapter 4.4) or diagnoses (attention deficit hyperactivity disorder, hyperkinetic disorders, hyperkinetic syndrome, hyperkinetic reaction of childhood or adolescence, overactive child syndrome and disturbance of activity and attention)
Autism spectrum disorder (ASD)	At least 1 diagnostic code ((infantile or childhood) autism, Asperger’s syndrome, Rett’s syndrome, Heller’s syndrome, Autistic spectrum disorder, disintegrative disorder, and other pervasive developmental disorders)
Major congenital malformation	Any- major system specific malformation according to the EUROCAT classification. We use Read code list mapped to ICD 10 codes Chapter Q. Exclude: 1) minor anomalies post-2005; 2) musculoskeletal malformations; 3) malformations caused by known chromosomal abnormalities and teratogens (i.e. Teratogenic syndromes with malformations, Fetal alcohol syndrome, Valproate syndrome, Maternal infections resulting in malformations, Genetic syndromes + microdeletions, Chromosomal malformations)
Cardiovascular malformation	1 Read code mapped from ICD 10 (Q20-Q26, exclude Q2111, Q250 if GA <37 weeks, Q2541, Q256 if GA<37 weeks, Q261)

Gastrointestinal malformation	Read code mapped from ICD 10 (Q38-Q45, Q790, exclude Q381, Q382, Q3850, Q400, Q401, Q4021, Q430, Q4320, Q4381, Q4382)
Nervous system malformation	Read code mapped from ICD 10 (Q00-Q07, exclude Q0461, Q0782)
Genital tract malformation	Read code mapped from ICD 10 (Q50-Q52, Q54-Q56, exclude Q523, Q525, Q527, Q5520, Q5521)
Urinary tract malformation	Read code mapped from ICD 10 (Q60-Q64, Q794, exclude Q610, Q627, Q633)

4.3.3 Covariates

We will control the covariates which are potential risk factors for adverse child outcomes. These include: 1) maternal characteristics at baseline (i.e. age at child birth, problematic alcohol use, illicit drug use, recent tobacco use, and obesity); 2) pregnancy related variables (i.e. birth year, parity, multiple birth, hypertension, diabetes, epilepsy, depression, anxiety, maternal chronic medical conditions during pregnancy, potentially fetal-damaging maternal infection during pregnancy, and baby gender) (details given below). Gestational age at delivery and Apgar score after birth are considered mediators on the pathway for the association between prenatal antibiotics exposure and adverse child outcomes and therefore not adjusted.

1. *Maternal variables*

1) **Maternal age (at birth)**

By 5 year categories.

2) **Maternal life style:**

a. Problematic alcohol use:

Most recent record between 10 years prior to and during pregnancy:

- a Read code indicating alcohol misuse; or
- a prescription for disulfiram or acamprosate; or
- self-reported average weekly alcohol intakes of between 14-500 units of alcohol a week.

b. Illicit drug use:

Most recent record between 10 years prior to and during pregnancy:

- a read code for drug use, addiction, and overdose; or
- a prescription for methadone treatment

c. Recent smoking/tobacco use:

Most recent record between 3 years prior to and during pregnancy:

- self-reported daily cigarette consumption of 1-100 cigarettes per day unless there was evidence of smoking cessation; or
- a read code indicating tobacco consumption; or
- a prescription to assist smoking cessation

d. Obesity

Most recent record from 3 years prior to the end of 1st trimester:

A read code for obesity (or a BMI of ≥ 30 kg/m² - either directly entered or calculated from the most recent height measurement and median pre-pregnancy weight after outliers, i.e. height outside the range 1-2m and weight outside the range 35-300kg, were removed).

2. *Pregnancy related variables*

3) **Baby birth year**

Grouped into categories of 5 calendar years.

4) **Parity**

Categorised as "0", and " ≥ 1 ".

5) **Multiple births**

Categorize the baby as "singleton", or "(one of the) twin, triplets, or quadruplets".

6) **Hypertension**

Measurement from 50 weeks prior to delivery:

- systolic and diastolic blood pressure was above 140mmHg and 90mmHg, respectively, or
- a Read codes for hypertension and associated diagnoses (including pre-eclampsia, eclampsia and HELLP syndrome), or
- a prescription for hypertension drugs from sections 2.2 and 2.5 of the BNF. This variable identified mothers with both treated and untreated hypertension in pregnancy.

7) **Diabetes**

Measurement from 50 weeks prior to delivery:

- a Read code for type I, type II, or gestational diabetes;
- two or more prescriptions for anti-diabetic medication; or
- laboratory tests indicative of diabetes (defined as ≥ 2 abnormal glucose tests, fasting glucose >7.0 millimoles per litre [mmol/L] or >126 milligrams per decilitre

[mg/dL], plasma glucose after glucose tolerance test >11.1 mmol/L or 200mg/dL, glycated haemoglobin \geq 6.5%, or with diabetes annual review).

8) Epilepsy

Measurement from 50 weeks prior to delivery: 2 prescriptions of antiepileptic drugs (AEDs) within 4 months or \geq 1 diagnosis

9) Depression

Measurement from 50 weeks prior to delivery: \geq 2 occurrences of diagnostic code, treatment code or symptom

10) Anxiety

Measurement from 50 weeks prior to delivery: \geq 2 occurrences of diagnostic code, treatment code or symptom

11) Treatment of chronic medical conditions during pregnancy

Measurement during pregnancy: two or more prescriptions (on separate days during pregnancy and not more than four months apart) for drugs from the same BNF section or paragraph. Drugs used to treat common conditions in pregnancy such as reflux (BNF section 1.2), nausea and vomiting (BNF section 4.6), and constipation (BNF section 1.3) were not included.

12) Potentially fetal-damaging infections during pregnancy.

Mothers are classified as having a potentially fetal-damaging infection in pregnancy if they had recorded at any time during their pregnancy, a Read code for a diagnosis or a laboratory test confirming any of the following infection: genitourinary infection, "TORCH" (Toxoplasmosis, Other agents such as HIV, Rubella, Cytomegalovirus and Herpes simplex) and sexually transmitted infections (STIs). "TORCH" and STIs have long been known as important risk factors to adverse pregnancy outcomes and teratogenic pathogens. (22, 23) Intrauterine infection has been recognised as an important mechanism of disease in preterm labor. (24) Hyelonephritis and bacteriuria have also been linked with preterm labor and low birthweight. (25)

3. Neonatal variables

13) Baby gender

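### The propensity score omits antibiotic use and GP contact before pregnancy although every outcome is GP-recorded, so residual bias of unknown size and direction may remain in the primary estimates

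*Combined protocol and SAP*

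**What the plan says.** **Covariates.** Section 4.3.3 of the combined protocol and SAP names "maternal characteristics at baseline (i.e. age at child birth, problematic alcohol use, illicit drug use, recent tobacco use, and obesity". The pregnancy-related items are "birth year, parity, multiple birth, hypertension, diabetes, epilepsy, depression, anxiety, maternal chronic medical conditions during pregnancy, potentially fetal-damaging maternal infection during pregnancy", plus baby gender. Section 4.4.1 estimates the score "conditional on the covariates described above, with the use of logistic-regression models". Neither list has a count of consultations, of other GP contacts, or of antibiotic courses before pregnancy.

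**Outcomes.** Section 4.3.2 defines neurodevelopmental disorders as "time to the first Read code or prescription indicating the outcomes by 14 years old". Malformations are "identified from child GP records up to 3 years old using Read codes". In Table 1, one diagnostic code is enough for ASD and two records are needed for ADHD.

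**Look-back.** Under section 4.2 each mother "had been registered with GP from at least 50 weeks before estimated conception date to delivery". Section 4.3.1 builds the negative control cohort from children whose mothers were "prescribed an only monotherapy of macrolides or penicillins during 10-50 weeks prior to conception and are not included in the study cohort".

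**The concern.** A family that sees its GP often has more chances for a diagnosis in the child to be coded. A mother with frequent infections may also be more, or less, likely to be given a macrolide rather than a penicillin. If both hold, GP use is linked to exposure and to recorded outcome, and a score that leaves it out cannot balance it. The balance check in 4.4.1 concerns the covariates, so it would not show an imbalance in a variable that is not listed.

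At stake are the primary hazard and risk ratios. A small bias matters most for the commoner outcomes, where the confidence interval is narrow enough for a few per cent to change the conclusion.

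**Working it through.** **1. Is the gap real?** The score uses only the 4.3.3 covariates. The nearest proxies there are treatment of chronic conditions (repeat prescribing during pregnancy, present or absent), depression and anxiety (two or more records each). None counts GP contacts or earlier antibiotic courses. The gap is real.

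**2. Are the data available?** To build the negative control cohort, antibiotic prescriptions 10-50 weeks before conception must be read. Every mother in the primary cohort has at least 50 weeks of registration before conception, so a prior-antibiotic count can be derived. For GP contacts the documents say less. Section 3 names prescriptions, diagnoses and symptoms, not consultation counts, so contacts may be derivable but are not shown to have been extracted.

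**3. How large could the bias be?** The plan gives no figure to reproduce. All inputs in this step are assumptions:
- pP, the share of frequent GP users in the penicillin group: 30%.
- pM, the share in the macrolide group after adjustment: 30% to 50%.
- d, the relative chance of a recorded outcome in children of frequent versus other users: 1.25 to 2.

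Bias factor B = [1 + pM(d − 1)] / [1 + pP(d − 1)]. It applies to the risk ratio, and approximately to the hazard ratio because the included baseline risks in Table 2 are at most 0.02.

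| pM | Standardized difference from 30% | d = 1.25 | d = 1.5 | d = 2 |
|---|---|---|---|---|
| 30% | 0 | 1.00 | 1.00 | 1.00 |
| 35% | 0.11 | 1.0875/1.075 = 1.01 | 1.175/1.15 = 1.02 | 1.35/1.30 = 1.04 |
| 40% | 0.21 | 1.10/1.075 = 1.02 | 1.20/1.15 = 1.04 | 1.40/1.30 = 1.08 |
| 50% | 0.42 | 1.125/1.075 = 1.05 | 1.25/1.15 = 1.09 | 1.50/1.30 = 1.15 |

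The 35% row lies just above the plan's own threshold of 0.1 for a meaningful imbalance. In the reverse direction, pM = 20% with d = 2 gives 1.20/1.30 = 0.92.

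**4. How does that compare with the precision?** Section 4.5 gives about 10,000 macrolide and 100,000 penicillin pregnancies. For a true ratio of 1, SE(log RR) = √[(1 − p)/(10,000p) + (1 − p)/(100,000p)], before any loss from weighting or clustering.
- Any major malformation, p = 0.02: SE = √(0.0049 + 0.00049) = 0.073, 95% CI 0.87-1.15.
- An outcome with p = 0.002: SE = √(0.0499 + 0.00499) = 0.234, 95% CI 0.63-1.58.

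Under a null effect with bias B, the two-sided rejection probability is 1 − Φ(1.96 − μ) + Φ(−1.96 − μ). Here μ = ln(B)/SE, with the SE recomputed at macrolide risk p × B.

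| B | p = 0.02 | p = 0.002 |
|---|---|---|
| 1.05 | 10% | 5.5% |
| 1.10 | 27% | 7% |

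**5. Can the same variables go into the negative control analysis?** There the index prescription falls t weeks before conception, with t from 10 to 50. Counts over the full 50 weeks would include the exposure itself and what followed it, so they would have to stop at the index date. Guaranteed look-back is then 50 − t weeks: 40 at t = 10 and 0 at t = 50. A raw count would depend on when the prescription fell.

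**The case against.** The design already limits this problem. Reference mothers also received an antibiotic, so the contrast is not between users and non-users of care. The single-monotherapy rule removes mothers with several separate or mixed courses in pregnancy. Depression, anxiety and repeat prescribing partly track GP use. Sensitivity analysis 2 restricts to respiratory infection. Cerebral palsy cases were validated by a specialist blinded to exposure, and musculoskeletal malformations are excluded as poorly recorded. One value of d for all outcomes is therefore only an illustration. Sensitivity analysis 1, the negative control, is aimed at confounding by maternal baseline characteristics, and a stable difference in GP use is what it should reveal. The illustrated bias is also small next to the 2-fold increase for which outcomes were screened in 4.5.

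Most of this stands as reason to expect a modest bias, but it does not fill the gap. The comparator and the monotherapy rule act during pregnancy: a mother with several courses in the year before and one with none are treated alike. The negative control uses other children and tests without correcting. The respiratory restriction addresses indication. The repeated-diagnosis definitions in sensitivity analysis 3 still depend on GP contact.

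A reader might infer that detection bias is known to be present, or that it must inflate the ratios. The documents support neither: they give no difference in GP use between the groups and no effect of GP use on recording. Nor do they support the inference that consultation counts are already in hand.

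**Conclusion.** The point holds as a possible residual bias, not a demonstrated one. The primary estimates are not adjusted for antibiotic use or GP contact before pregnancy, although recording of every outcome depends on GP records. The bias may be nil, upward or downward. On the assumed inputs it runs from 1.00 to 1.04 for gaps of up to 5 percentage points and reaches 1.15 only at 50% versus 30% with a doubled chance of recording. These gaps are taken as wholly residual after adjustment, so they are generous if the listed covariates capture part of GP use. It matters most for any major malformation and least for outcomes with a risk near 0.002. The change is worth making because it is cheap and uses variables that precede exposure, not because bias has been shown.

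**What to change.** For the primary cohort, add two variables to 4.3.3, the propensity score and the balance table, both measured in the 50 weeks before estimated conception:
- Number of antibiotic courses of any class (0, 1, 2, 3 or more). An any-class count is preferable to prior macrolide use, which may predict exposure strongly without bearing on outcome.
- Number of maternal GP contacts. If consultation counts are not available, use the number of dates with any record as a proxy.

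Report results from the score as now listed in 4.3.3 alongside, as a named sensitivity analysis, so that readers see what the addition changes.

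Do not require these variables in the negative control analysis as planned, because guaranteed look-back there is only 0 to 40 weeks. Either omit them and say so, or restrict that adjustment to mothers with enough earlier registration.

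The cost is two derived variables, the second subject to a check on availability, and slightly more trimming of non-overlapping scores.
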